7.3 Prior and Concomitant Medications

[figure not shown]
Medication terms will be coded using the World Health Organization (WHO) Drug Dictionary (Version WHODDMAR21B3G). The version of the dictionary will be noted in the statistical tables and clinical study report.

A prior medication is defined as any medication taken prior to the date of the first dose of study intervention. A concomitant medication is defined as any medication that starts prior to the date of the first dose of study intervention and continues to be taken after the first dose of study intervention or any medication that starts on or after the date of the first dose of study intervention.

The number and percentage of participants taking medications will be summarized by preferred drug name based on the World Health Organization (WHO) Drug Dictionary for both prior and concomitant medications, respectively.

8.4 Efficacy Subgroup Analyses

No subgroup analyses are planned.

9.0 Safety Analyses

9.1 General Considerations

The below general considerations will be applied to safety analyses, unless specified otherwise.

• Safety analyses will be based on safety data using the safety population based on the actual treatment received.

- A participant's actual treatment will be determined by the first dose of study drug.
- In general, baseline is defined as the last non-missing scheduled assessment prior to the first administration of study intervention (non-missing assessment before Day 1 study intervention).
- The change from baseline values at a visit will be computed as the value for the post baseline visit minus the baseline value, unless otherwise indicated.
- Descriptive statistics for continuous variables include the sample size (n, mean, standard deviation, median, 1st and 3rd quartiles, minimum, and maximum).
- Summary statistics for categorical variables include the sample size (n), frequency count, and percentage.
- AEs and findings from biomicroscopy and ophthalmoscopy examinations will be coded using the Medical Dictionary for Regulatory Activities (MedDRA) version 24.1 or higher, according to the version of the MedDRA coding dictionary used for the study at the time of database lock.

[figure not shown]
9.2 Adverse Events

AEs will be summarized and presented using primary MedDRA SOCs and preferred terms (PTs). Specific adverse events will be counted once for each participant for calculating percentages, unless stated otherwise. In addition, if the same adverse event occurs multiple times for a participant, the highest severity and level of relationship to investigational product will be reported.

9.2.1 Treatment-Emergent Adverse Events

An AE will be considered a treatment-emergent adverse event (TEAE) if the AE began or worsened (increased in severity or became serious) on or after the date of the first dose of study drug. Events where the onset date is the same as the study drug start date are assumed to be treatment emergent.

In general, the number and percentage of participants experiencing TEAEs will be summarized overall, as well as by primary MedDRA SOC and PT. The SOCs will be

presented in alphabetical order, and the PTs will be presented in decreasing frequency order on active study drug within each SOC. The number and percentage of participants experiencing TEAEs will also be summarized by PT for identifying common AEs. TEAEs by PT summaries will be presented in decreasing frequency order on active study drug.

9.2.2 Adverse Event Overview

Adverse events will be classified into ocular AEs and non-ocular AEs. An ocular AE will be determined as indicated on the AE form of eCRF (marked "OD" or "OS" to the question of "what was the location of the adverse event?"), and thus are not limited to AEs with primary SOCs of eye disorders.

An overview of AEs will be presented consisting of the number and percentage of participants experiencing at least one event for each of the following AE categories:

- TEAEs
 - Ocular TEAEs
 - Non-ocular TEAEs
- TEAEs related to study drug
 - Ocular TEAEs related to study drug according to the investigator
 - Non-ocular TEAEs related to study drug according to the investigator
- Severe TEAEs
- Serious TEAEs
 - Ocular serious TEAEs
 - Non-ocular serious TEAEs
- TEAEs leading to withdrawal of study treatment
 - Ocular leading to withdrawal of study treatment
 - Non-ocular leading to withdrawal of study treatment
- TEAEs of special interest
- TEAEs leading to death

- All deaths
- COVID-19 infection.

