1.2. Schema

Study flow diagrams for Stages 1 and 2 of the study are presented in Figure 1-1 and Figure 1-2.

Figure 1-1 Study Flow Diagram – Stage 1

Visit 4 – 0.5 hours postdose

[figure not shown]

BID = twice daily; DMC = data monitoring committee; PK = pharmacokinetics; QD = once daily

Visit 5 – 0 hour (predose) and at 0.5.2.4.8. and 12 hours postdose

Figure 1-2 Study Flow Diagram - Stage 2

On Day 1, participants will be randomized 1:1:1:1:1 to the 5 study intervention groups shown.

The study eye will be defined as the eye with the highest . If both eyes qualify and have the If both eyes still qualify, the right eye will be designated as the study eye.

BID = twice daily; CAE = controlled adverse environment; OU = both eyes;

; PK = pharmacokinetic(s)

[figure not shown]

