6.1.1. Dosing Regimen

6.1.1.1. Dosing Regimen in Stage 1

Stage 1 includes up to 3 consecutive cohorts, with 24 participants in each cohort. Participants from 1 cohort will not be allowed to enroll into the subsequent cohort(s). Participants in each cohort will be randomized into 1 of 4 intervention arms:

- AGN-242428 (N = 9)
- AGN-231868 (N = 9)
- AGN-242428 vehicle (N = 3)
- AGN-231868 vehicle (N = 3)

The morning dose of the assigned study intervention will be administered by the site staff at Visits 2, 3, 4, and 5 (except for Early Termination visit).

All participants will receive 1 drop of the assigned intervention to the left eye on Day 1 (Visit 2) (administered by the site staff). On Days 2 to 14, the participants will administer a single drop to both eyes, twice daily (approximately 12 hours apart). On Day 15 (Visit 5), the participants will be administered a single dose to both eyes.

6.1.1.2. Dosing Regimen in Stage 2

In Stage 2,

approximately 250 participants, who requalify at Baseline visit, will be randomized into 5 groups, in a 1:1:1:1:1 ratio within each site, as follows:

- AGN-242428 (N = 50)
- AGN-242428 vehicle (N = 50)
- AGN-231868 (N = 50)
- AGN-231868 vehicle (N = 50)
- Xiidra (N = 50)

The morning dose of the assigned study intervention will be administered by the unmasked site staff at Visits 2, 3, 4, 5, and 6. Any masked staff members should not be present in the room during dosing to prevent unmasking.

During the intervention period, participants will be instructed to administer 1 drop of assigned intervention twice daily (approximately 12 hours apart) to both eyes on Days 1 to 41. On Day 42, the participants will be administered a single dose to both eyes. The highest tolerated doses of AGN-242428 and AGN-231868 (established in Stage 1) will be selected for testing in Stage 2 to maximize the potential to achieve proof of concept.

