3.0 Endpoints

3.1 Safety Endpoints

Safety endpoints are listed as the following:

AGN-242428 and AGN-231868 2012-201-005 – Statistical Analysis Plan (Stage 2) Version 1.0 – 07 December 2021

- adverse events (AEs),
- clinical laboratory values at the Exit/Early Termination visit,
- vital signs at each post-baseline visit,
- electrocardiogram (ECG) findings at the Exit/Early Termination visit,
- intraocular pressure (IOP) at each post-baseline visit,
- best-corrected visual acuity (BCVA) at each post-baseline visit,
- slit-lamp biomicroscopy findings at each post-baseline visit,
- dilated fundus (ophthalmoscopy) examination findings at the Exit/Early Termination visit.
- Drop Tolerability Questionnaire score at each post-baseline visit.

For eye-related endpoints, both eyes will be included in the analysis.

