7.2 Medical History

Medical history including prior procedures data will be coded using the Medical Dictionary for Regulatory Activities (MedDRA), version 24.1 or higher. The actual version of the MedDRA coding dictionary will be noted in the statistical tables and clinical study report.

The number and percentage of participants in each medical history category (by MedDRA primary system organ class and preferred term) will be summarized. The system organ class (SOC) will be presented in alphabetical order, and the preferred terms will be presented in alphabetical order within each SOC. Participants reporting more than one condition/diagnosis will be counted only once in each row (SOC or preferred term).

[figure not shown]
An ophthalmic history will be determined as indicated on the Medical History form of eCRF (marked "OD," "OS," or "OU" to the question of "What was the location of the medical history condition/event?"). The ophthalmic medical history will be summarized in a similar way to medical history.

[figure not shown]

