9.2.3 Treatment-Emergent Adverse Events by SOC and/or PT

Treatment-emergent adverse events will be summarized for each of the following AE categories:

[figure not shown]
- TEAEs by SOC and PT
 - Ocular TEAEs by SOC and PT
 - Non-ocular TEAEs by SOC and PT
- TEAEs by PT
- TEAEs related to study drug by SOC and PT
 - Ocular TEAEs related to study drug by SOC and PT
 - Non-ocular TEAEs related to study drug by SOC and PT
- TEAEs by SOC, PT, and maximum severity
 - Ocular TEAEs by SOC, PT, and maximum severity
 - Non-ocular TEAEs by SOC, PT, and maximum severity

Specific adverse events will be counted once for each participant for calculating percentages, unless stated otherwise.

If the same adverse event occurs multiple times for a participant, the highest severity and level of relationship to investigational product will be reported.

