9.2.4 SAEs (Including Deaths) and Adverse Events Leading to Study Drug Discontinuation

SAEs (including deaths) and AEs leading to study drug discontinuation will be summarized by SOC and PT and in listing format.

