Appendix E. Changes to Protocol-planned Analyses

No statistical comparisons/tests among the study intervention groups will be performed for the safety data.

Safety Statistical Analysis Plan

2012-201-005 [Stage 1]

Title Page

Protocol Title:

A Multicenter, Vehicle-controlled, Double-Masked, Randomized Study to Evaluate the Safety, Tolerability, Pharmacokinetics, and Exploratory Efficacy of AGN-242428 and AGN-231868 in Participants with Dry Eye Disease

Protocol Number: 2012-201-005 [Stage 1]

Compound Number: AGN-242428 and AGN-231868

Short Title:

Safety, Tolerability, Pharmacokinetics, and Efficacy of AGN-242428 and AGN-231868 in

Participants with Dry Eye Disease

Sponsor Name: Allergan Sales LLC

Legal Registered Address: [name]

Regulatory Agency Identifier Number(s)

Registry ID

IND 139391, 139392

Table of Contents

Title Pag	Je	
Table of	Contents	2
List of T	ables	3
SAP Vei	rsion History	4
1.	Introduction	
1. 1.1.	Objectives and Endpoints	
1.2.	Study Design	
2.	Statistical Hypotheses	8
3.	Sample Size Determination	9
4.	Analysis Sets	10
5.	Statistical Analyses	11
5.1.	General Considerations	
5.2.	Participant Disposition.	12
5.3.	Primary Endpoint(s) Analysis	
5.4.	Secondary Endpoint(s) Analysis	13
5.5.		13
5.6.	Safety Analyses	13
5.6.1.	Extent of Exposure	13
5.6.2.	Adverse Events	14
5.6.2.1.	Adverse Events of Special Interest	15
5.6.3.	Additional Safety Assessments	16
5.6.3.1.	Clinical Laboratory Parameters	16
5.6.3.2.	Potential Hy's Law	17
5.6.3.3.	Vital Signs	17
5.6.3.4.	Electrocardiogram	18
5.6.3.5.	Physical Exam.	19
5.6.3.6.	Best-corrected Visual Acuity	19
5.6.3.7.	Intraocular Pressure	20
5.6.3.8.	Biomicroscopy	20
5.6.3.9.	Dilated Fundus Examination.	21
	Drop Tolerability Questionnaire Score	
5.7.	Other Analyses	
5.7.1.	Other Variables and/or Parameters	22
5.7.1.1.	Pharmacokinetic Analyses	22
5.7.2.	Subgroup Analyses	
5.8.	Interim Analyses	22
5.8.1.	Data Monitoring Committee	22

Safety Statistical Analysis Plan

2012-201-005 [Stage 1]

6.	Supporting Documentation	23				
6.1.	Appendix 1: List of Abbreviations					
6.2.	Appendix 2: Changes to Protocol-planned Analyses					
6.3.	Appendix 3: Supporting Study Information					
6.3.1.	1. Demographics					
6.3.2.	Baseline and Disease Characteristics					
6.3.3.	Protocol Deviations.	27				
6.3.4.	Medical and Ophthalmic History					
6.3.5.	Prior/Concomitant Medications (Including Dictionary)					

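### The Stage 2 SAP counts an adverse event as ocular only if its location is marked OD or OS; if the AE form also offers OU, bilateral eye events would be tabulated as non-ocular

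*SAP*

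**What the plan says.** Stage 2 SAP section 9.2.2 divides adverse events into two classes, ocular and non-ocular, with no third category. The test is the location recorded on the AE form: "An ocular AE will be determined as indicated on the AE form of eCRF (marked 'OD' or 'OS' to the question" asking for the event's location. The section adds that ocular events therefore need not belong to the eye-disorders system organ class.

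Section 7.2 of the same SAP makes a parallel classification for ophthalmic history from a similar question on the Medical History form, but with three qualifying answers: "marked 'OD,' 'OS,' or 'OU' to the question of 'What was the location of the medical history condition/event".

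OU has a defined meaning in this study. The legend of the Stage 2 flow diagram (Protocol 1.2) reads "CAE = controlled adverse environment; OU = both eyes". Treatment is bilateral: under Protocol 6.1.1.2, "participants will be instructed to administer 1 drop of assigned intervention twice daily (approximately 12 hours apart) to both eyes". SAP 3.1 states the intention for eye endpoints: "For eye-related endpoints, both eyes will be included in the analysis".

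The split feeds the overview in 9.2.2 and a set of tables in 9.2.3, for example "Ocular TEAEs by SOC, PT, and maximum severity".

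**The concern.** The same SAP gives two different rules for the same kind of classification and does not explain the difference. Read literally, the AE rule leaves out the one response code that describes an event in both eyes, in a trial where both eyes are dosed. With only two classes, an event that fails the ocular test is non-ocular by default.

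Safety and tolerability is the primary objective of Stage 2, and for an eye drop the ocular AE tables are the most direct AE summary of local safety. If OU-marked events are excluded, the ocular rows for all, related, serious and withdrawal-related TEAEs, and the ocular tables by SOC and PT, by relationship and by maximum severity, would be too low. The matching non-ocular outputs would tend to be too high. Because the SAP recognises that ocular events can be coded outside the eye-disorders class, the SOC and PT tables alone would not show a reader every event that occurred in an eye.

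**Working it through.** The plan gives no figure on this point to reproduce. The check is a comparison of text, followed by an illustration of size.

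**1. The two rules side by side**

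| | Ophthalmic history (SAP 7.2) | Ocular AE (SAP 9.2.2) |
|---|---|---|
| Source | Medical History form, location question | AE form, location question |
| Qualifying answers | OD, OS, OU | OD, OS |
| Fallback by SOC | none stated | none stated |

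Nothing else in the supplied SAP or protocol text defines an ocular AE, adds OU to the AE rule, or makes an eye-disorders event ocular whatever location is marked. The Stage 1 SAP has no ocular/non-ocular split, so it offers no precedent.

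**2. The rule applied to a bilateral eye event**

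- If the AE form has OU as a separate response and it is chosen, the event is marked neither OD nor OS, fails the test and becomes non-ocular.
- If the form has only OD and OS, and bilateral events are entered as two ticks or two records, the event passes and nothing is misclassified.

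The documents do not reproduce the AE form, so they do not settle which case applies.

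**3. Illustrative size if OU is an option**

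Inputs:
- n = 50 per arm (Protocol 6.1.1.2).
- r = true proportion with at least one ocular AE, assumed 5% to 25%. Protocol 6.3.2 quotes the same span for certain reactions to Xiidra, one of which (dysgeusia) is not ocular, so it is not an estimate of r.
- b = share of those participants whose ocular AEs are all marked OU, assumed 20% to 90%. Anyone with at least one OD or OS event stays in the overall ocular row.

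Participants leaving the ocular row per arm = n × r × b:

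- b = 20%: 50 × 0.05 × 0.2 = 0.5, to 50 × 0.25 × 0.2 = 2.5
- b from 50% to 90%: 50 × 0.05 × 0.5 = 1.25, to 50 × 0.25 × 0.9 = 11.25

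The non-ocular row gains at most the same number, since some of these participants may already be counted there.

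**4. Effect on an active-versus-vehicle contrast**

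Reported rate = r × (1 − b). With the same b in both arms, the reported difference is the true difference × (1 − b), and the ratio does not change. With assumed true rates of 20% and 8%:

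| b | Active | Vehicle | Difference (points) | Ratio |
|---|---|---|---|---|
| 0 | 20% | 8% | 12 | 2.5 |
| 20% | 16% | 6.4% | 9.6 | 2.5 |
| 50% | 10% | 4% | 6 | 2.5 |
| 90% | 2% | 0.8% | 1.2 | 2.5 |

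A bias that differs between arms would need b to differ between arms. Nothing in the documents shows that it would.

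**The case against.** The strongest reply is that the only evidence about the AE form is 9.2.2 itself, which names OD and OS. Section 7.2 describes another form with its own question, so the two lists may simply reflect two forms with different options. Elsewhere the study records by eye: tear samples are logged as right or left, and the protocol's abbreviation list defines OD and OS but not OU. The remark about not being limited to eye-disorders classes, together with SAP 3.1, suggests that a bilateral eye event was meant to be ocular. An eye-disorders class appearing in a non-ocular table would probably be noticed.

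The harm is also bounded. The unsplit TEAE tables and the AESI and death rows keep every event. SAP 9.2.4 is not split by ocular status: "SAEs (including deaths) and AEs leading to study drug discontinuation will be summarized by SOC and PT and in listing format". Appendix E adds: "No statistical comparisons/tests among the study intervention groups will be performed for the safety data". Finally, the rates and shares used above are assumptions, and the largest figures come from the extreme corner of the range.

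Most of this stands: the form is unseen, the size is unknown, and total counts are not at risk. It does not remove the gap. Evidence of intent does not alter the stated test, which rests on location alone. Nor does the supplied text say how a bilateral event is recorded, so a reader cannot confirm that the rule is complete. Relying on someone to notice the error means correcting a primary-objective output after the data have been seen.

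**Conclusion.** The concern holds as a conditional one. It is certain that 9.2.2 omits OU while 7.2 accepts it, and that nothing in the supplied text closes the gap. Whether any event would be misclassified depends on the AE form: there is no effect if it has no OU response or if bilateral events are entered under each eye.

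If OU is a response, the ocular outputs are understated. Under the assumed rates, the loss runs from about 0.5 participants per arm (5% rate, b = 20%) to about 11.3 (25% rate, b = 90%). Absolute differences between active and vehicle shrink by the factor 1 − b, and ratios are preserved when b is equal across arms. No reversal or differential bias is shown. The point is worth fixing because it touches a primary-objective output and can be settled before lock, but it does not threaten the overall safety counts.

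**What to change.** Before database lock, look at the response options for the location question on the AE form. In Stage 2 SAP 9.2.2, define an ocular AE as one whose location is marked OD, OS or OU, in line with 7.2. If the form turns out to have no OU response, the added term has no effect, and a sentence saying how bilateral events are recorded would serve the reader as well. The rule of counting each participant once is already in 9.2 and 9.2.3 and needs no change.

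The cost is one term in the SAP, the same term in the AE derivation program, and a look at the form. No new data are needed.

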9.2.3 Treatment-Emergent Adverse Events by SOC and/or PT

Treatment-emergent adverse events will be summarized for each of the following AE categories:

[figure not shown]
- TEAEs by SOC and PT
 - Ocular TEAEs by SOC and PT
 - Non-ocular TEAEs by SOC and PT
- TEAEs by PT
- TEAEs related to study drug by SOC and PT
 - Ocular TEAEs related to study drug by SOC and PT
 - Non-ocular TEAEs related to study drug by SOC and PT
- TEAEs by SOC, PT, and maximum severity
 - Ocular TEAEs by SOC, PT, and maximum severity
 - Non-ocular TEAEs by SOC, PT, and maximum severity

Specific adverse events will be counted once for each participant for calculating percentages, unless stated otherwise.

If the same adverse event occurs multiple times for a participant, the highest severity and level of relationship to investigational product will be reported.

9.2.4 SAEs (Including Deaths) and Adverse Events Leading to Study Drug Discontinuation

SAEs (including deaths) and AEs leading to study drug discontinuation will be summarized by SOC and PT and in listing format.

9.2.5 Adverse Events of Special Interest

Summary table by PT will be provided for Adverse Events of Special Interest (AESI) as defined in Appendix B, which will also be provided in a listing.

9.3 Analysis of Laboratory Data

Descriptive statistics for values and changes from the baseline in standard units at each assessment time point will be presented by study intervention group.

Clinical laboratory test values will be considered potentially clinically significant (PCS) if they meet either the lower-limit or upper-limit PCS criteria listed in Appendix C. The number and percentage of participants who have PCS post-baseline clinical laboratory values will be tabulated by study intervention for all scheduled postbaseline visit. The percentages will be calculated relative to the number of participants who have available non-PCS baseline values and at least 1 postbaseline assessment. The numerator will be the total number of participants with at least 1 PCS postbaseline value.

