9.4 Analysis of Vital Signs

Descriptive statistics for vital signs (systolic and diastolic blood pressure, pulse rate, weight, respiration rate, and temperature) and their changes from baseline at each assessment timepoint will be presented by study intervention group.

Selected vital signs will be considered potentially clinically significant (PCS) if they meet either the lower-limit or upper-limit PCS criteria listed in Appendix C. The number and percentage of participants who have PCS postbaseline vital sign values will be tabulated by study intervention for each postbaseline visit assessments. The percentages will be calculated relative to the number of participants who have available baseline values for those parameters with the change from baseline value criterion or non-PCS baseline values for those vital sign parameters without the change from baseline value criterion and at least 1 postbaseline assessment. The numerator will be the total number of participants with at least 1 PCS postbaseline value.

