Weight		Low		Decrease of ≥ 7%
Dagninatam, Data	hom	High	≥ 28	_
Respiratory Rate	bpm	Low	≤ 8	_
Tommoroturo	°C	High	> 38	_
Temperature		Low	< 35	_

BP = blood pressure; bpm = beats/breaths per minute

ECG values meeting *either* the actual value or change from baseline PCS high criteria will be categorized as PCS.

[figure not shown]
[figure not shown]

Table 8. Potentially Clinically Significant Criteria for ECG Parameters

[figure not shown]
Parameter		PCS High Criteria		
	Unit	Actual Value	Change from Baseline	
QRS interval	msec	≥ 150	_	
PR interval	msec	≥ 250	_	
QTcF	msec	> 500	Increase > 60	

QTcF = QTc Fridericia

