5.6.3. Additional Safety Assessments

5.6.3.1. Clinical Laboratory Parameters

Table 5-6 Safety Laboratory Assessments

Laboratory			
Assessments	·		
Hematology	Platelet count	RBC indices:	WBC count with differential (absolute):
	RBC count	MCV	Neutrophils
	Hemoglobin	MCH	Lymphocytes
	Hematocrit	MCHC	Monocytes
			Eosinophils
			Basophils
Clinical Chemistry ^a	BUN	Potassium	Aspartate aminotransferase (AST)
	Creatinine	Sodium	Alanine aminotransferase (ALT)
	Glucose (fasting ^b) Calcium Alkaline phosphatase		Alkaline phosphatase
	Total protein	Cholesterol	Total, direct and indirect bilirubin
	Albumin	Chloride	
Routine Urinalysis	Specific gravity, pH, glucose, protein, blood, ketones, bilirubin, urobilinogen, nitrite,		
,	leukocyte esterase by dipstick		
	Microscopic examination (if blood or protein is abnormal)		

^a In Stage 1, blood samples will be collected following 10-hour fasting period.

Descriptive statistics for quantitative clinical laboratory values (in SI units) at Screening, Exit visit, and changes from baseline at Exit/Early Termination visit will be presented by cohort and study intervention group for each clinical laboratory assessment.

Clinical laboratory test values will be considered PCS if they meet either the lower-limit or higher-limit PCS criteria listed in Table 6-5. The number and percentage of participants who have at least one PCS post-baseline clinical laboratory values will be tabulated by cohort and study intervention group at Exit visit. The percentages will be calculated based on the denominator of the number of participants with available non-PCS baseline values and at least one post-baseline value and the numerator of the number of participants with non-PCS baseline value and at least one PCS post-baseline-value.

^b Fasting requirement is for Stage 1 only

Safety Statistical Analysis Plan

2012-201-005 [Stage 1]

A supportive listing of participants with postbaseline PCS values will be provided, including the participant number and baseline and postbaseline values, for the safety population. A listing of conversion factors to convert SI units to conventional units will be provided.

Table 5-7 Clinical Laboratory Summaries

Endpoint	Description	Timing	Methodology

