PCS values ^a	 Summary by laboratory category, laboratory test, and PCS criteria Participants with baseline PCS values excluded from analysis Parameters and PCS criteria specified in Sections 6.5.2.2 and 6.5.2.1, respectively 	Screening ^b , Exit ^c	PCS descriptives/ Supportive data listing
Descriptives	Summary by laboratory category and laboratory test in SI and /or CV units and analysis visit Parameters specified in Section 6.5.2.2	Screening ^b , Exit ^c	CFB descriptives

^a Participants who report ≥ 1 postbaseline PCS value and all clinical laboratory for those participants will be listed.

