5.6.3.3. Vital Signs

Descriptive statistics for vital signs (systolic and diastolic blood pressures, pulse rate, weight, respiration rate, and temperature) at Screening, Baseline (Day 1) and changes from baseline values at each visit and at the Exit/Early Termination visit will be presented by cohort and study intervention group.

^b Visit will be used as baseline for change from baseline summaries.

^c Exit: Final or early termination visit.

Safety Statistical Analysis Plan

2012-201-005 [Stage 1]

Vital sign values will be considered PCS if they meet either the lower-limit or higher-limit PCS criteria listed in Table 6-6. The number and percentage of participants who have at least one PCS post-baseline vital sign value will be tabulated by cohort and study intervention group. The percentages will be calculated based on the denominator of the number of participants with available baseline values or non-PCS baseline values (respiratory rate and temperature) and at least one post-baseline value and the numerator of the number of participants with non-PCS baseline value and at least one PCS post-baseline value.

A supportive listing of participants with postbaseline PCS values will be provided, including the participant number and baseline and postbaseline values, for the safety population.

Table 5-9 Vital Signs Summaries

Endpoint	Description	Timing	Methodology
PCS values ^a	Summary by parameter and PCS criteria Denominator: available baseline or non-PCS baseline (respiratory rate or temperature) and at least one end-of-study or postbaseline values Parameters and PCS criteria specified in Sections 6.5.3.2	Blood pressure, pulse rate, temperature: Day 1 ^b , Day 2, Day 8, Exit ^c Respiration rate, weight: Screening ^b , Exit ^c	PCS descriptives/ Supportive data listing ^a
Descriptives	and 6.5.3.1 respectively Summary by parameter and analysis visit Parameters specified in Section 6.5.3.2	Blood pressure, pulse rate, temperature: Screening, Day 1 ^b , Day 2, Day 8, Exit ^c Respiration rate, weight: Screening ^b , Exit ^c	CFB descriptives

^a Participants who report ≥ 1 postbaseline PCS value and all vital signs will be listed.

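### Stage 2 PCS percentages for laboratory, ECG, respiratory rate and temperature remove participants who are PCS at baseline from the denominator but not from the numerator, so the rates can only err upward

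*SAP*

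**What the plan says.** **Stage 2 SAP, laboratory (9.3).** The denominator is set by "The percentages will be calculated relative to the number of participants who have available non-PCS baseline values and at least 1 postbaseline assessment". The sentence after it sets the numerator: "The numerator will be the total number of participants with at least 1 PCS postbaseline value".

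**Stage 2 SAP, ECG (9.5).** The same two sentences appear. Under Appendix C, an ECG value that meets "the actual value or change from baseline PCS high criteria will be categorized as PCS". QRS and PR have actual-value limits only. QTcF has an actual-value limit (> 500 msec) and a change limit (increase > 60 msec).

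**Stage 2 SAP, vital signs (9.4).** There are two denominators. Parameters with a change-from-baseline criterion use any available baseline. The others use "non-PCS baseline values for those vital sign parameters without the change from baseline value criterion and at least 1 postbaseline assessment"; by Appendix C, Table 7, these are respiratory rate and temperature. The numerator sentence is the same as in 9.3.

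**Protocol 9.4.2.2 to 9.4.2.4.** The same unrestricted numerator sentence is used for laboratory, vital signs and ECG.

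**Stage 1 SAP.** For laboratory data, 5.6.3.1 specifies "the numerator of the number of participants with non-PCS baseline value and at least one PCS post-baseline-value", and Table 5-7 adds "Participants with baseline PCS values excluded from analysis". Section 5.6.3.4 and Table 5-11 do the same for ECG. The Stage 2 SAP has no equivalent statement.

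**Use of the tables.** Stage 2 SAP Appendix E states: "No statistical comparisons/tests among the study intervention groups will be performed for the safety data".

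**The concern.** A percentage needs a numerator drawn from its denominator. Read literally, the Stage 2 rule breaks this for anyone who is PCS at baseline (or has no baseline value) and PCS at a later visit, because that person adds to the count but not to the number at risk. A persistent pre-existing abnormality, such as total cholesterol above 1.2 x ULN, would then raise what readers take to be a rate of new PCS values on treatment.

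Laboratory values, vital signs and ECG findings all serve the Stage 2 primary objective. With no between-group safety test planned, readers will compare each drug with its vehicle by eye from these tables. A chance imbalance in baseline abnormality between arms could then look like a drug effect. The two stages of one study would also define the same percentage differently.

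**Working it through.** The plan states no PCS rate, so there is no figure of its own to reproduce.

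**Inputs from the documents.** 50 participants per Stage 2 arm (Protocol 6.1.1.2). ECG in about 20% of Stage 2 participants, with no fewer than 10 per arm (Protocol 8.1.7).

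**Inputs that must be assumed.** The baseline PCS count b, the share q of those who are PCS again afterwards (so k = q x b), and the number of new cases x.

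**Formulas**, for n participants with a baseline and at least one postbaseline value:
- Rate as written = (x + k)/(n - b)
- Rate with a matched numerator = x/(n - b)
- Excess = k/(n - b) = q x b/(n - b), which is never negative

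**Excess, n = 50**

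| b | q = 0.5 | q = 1 |
|---|---|---|
| 1 | 0.5/49 = 1.0 points | 1/49 = 2.0 points |
| 3 | 1.5/47 = 3.2 points | 3/47 = 6.4 points |
| 5 | 2.5/45 = 5.6 points | 5/45 = 11.1 points |

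**Example.** With x = 2 and b = 3, the matched rate is 2/47 = 4.3%. As written it is (2 + 1.5)/47 = 7.4% at q = 0.5 and (2 + 3)/47 = 10.6% at q = 1.

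**ECG subset, n = 10.** With b = 1, k = 1 and x = 0, the rate as written is 1/9 = 11.1% and the matched rate is 0%.

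**No upper bound.** With n = 50, b = 26, k = 25 and x = 0, the rate as written is 25/24 = 104.2%. These counts are unrealistic, but they show that the ratio is not a proportion.

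**Chance imbalance between two arms of 50, no drug effect.** In each arm independently, b ~ Binomial(50, p), k given b ~ Binomial(b, q), and x ~ Binomial(50 - b, e). Exact enumeration gives the probability that the two reported rates for one parameter differ by at least 5 points. Each as-written range covers q = 0.5 to q = 1.

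| Baseline prevalence p | As written, e = 0 | As written, e = 4% | Matched, e = 4% |
|---|---|---|---|
| 2% | 0.018 to 0.072 | 0.24 to 0.28 | 0.19 |
| 6% | 0.139 to 0.289 | 0.33 to 0.43 | 0.18 |
| 10% | 0.284 to 0.469 | 0.42 to 0.55 | 0.18 |

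With e = 0 the matched difference is always 0, because no new cases are allowed. The e = 4% columns are the fairer comparison: ordinary sampling variation already gives 0.18 to 0.19, and the rule as written adds to that.

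**Scope.**
- Blood pressure and pulse rate are not affected. Protocol 9.4.2.3 requires both the observed-value and the change criterion, and their denominator is any available baseline.
- Weight has only a change criterion, so it is not affected either.
- For ECG, the actual-value limits can be met at baseline; the QTcF increase criterion cannot.

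**The case against.** The strongest reply is that this is an ambiguity and not an intended rule. A percentage taken relative to a group naturally implies a numerator from that group. The sponsor seems to have read it so: the Stage 1 SAP restricts the numerator, and its 6.2 (Appendix 2) still declares no change from the protocol-planned analyses. That SAP follows Amendment 2, and the text available here is Amendment 3, so this is good evidence of intent but not proof. Table specifications are in a separate document. It does not settle the matter, because the Stage 2 text refers to the total number and nothing else in that SAP narrows it.

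Other points stand in part:
- Eligibility requires good general health and excludes laboratory abnormalities judged clinically significant at screening (Protocol 5.2.1 and 8.1.8). Baseline PCS temperature, respiratory rate or QTcF should therefore be rare. These are investigator judgements and not PCS limits, so milder laboratory abnormalities can still be present.
- The missing-baseline route is nearly empty, since baseline is the last non-missing scheduled value before dosing and these assessments are scheduled at screening.
- At low baseline prevalence, most of the chance of a 5-point gap is sampling noise, and the 5-point threshold is a choice made for illustration.
- Values and changes from baseline are also summarised, and adverse events, including liver events of special interest, are reported separately.

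These points limit the likely size and consequence. They do not make the stated rule correct.

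**Conclusion.** The rule is wrong as written for laboratory and ECG, and for respiratory rate and temperature among the vital signs. It counts people outside its own denominator, and the error can only be upward. A restricted numerator may well have been intended, but the Stage 2 SAP does not say so.

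The size depends on baseline PCS prevalence and persistence, which the documents do not give. If nobody is PCS both before and after dosing, there is no error. One to five such baseline cases in an arm of 50, with half to all persisting, add about 1 to 11 points. The effect is confined to descriptive tables, with no test or decision rule depending on them. The point should be fixed because the tables report primary-objective safety endpoints and the correction is trivial.

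**What to change.** - **9.3, 9.5, and 9.4 for respiratory rate and temperature:** define the numerator as participants in the denominator (non-PCS baseline and at least one postbaseline assessment) who have at least one PCS postbaseline value. This matches the Stage 1 laboratory and ECG rule.
- **9.4, blood pressure, pulse rate and weight:** for completeness, state the numerator as participants with an available baseline and at least one PCS postbaseline value. Do not copy the Stage 1 vital-sign sentence (Stage 1 SAP 5.6.3.3), which uses "the numerator of the number of participants with non-PCS baseline value and at least one PCS post-baseline value" for every parameter while its denominator for these three needs only an available baseline.
- **Appendix E:** record the point, since Protocol 9.4.2.2 to 9.4.2.4 carry the unrestricted sentence. If the sponsor regards the edit as a clarification of intent, the entry can say so.
- **Table specifications:** check that they follow the same rule.

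The cost is one sentence in each of three SAP subsections and one Appendix E entry. No new data and no protocol amendment are needed.
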